4.5.3. Data Collection for Non-eligible Infants

To complete the patient flow description, this protocol addresses infants in the inclusion GA who are not eligible to be randomized. By definition this includes infants whose parent has refused to consent. We seek approval to capture limited data for this group of infants. There are two reasons for collecting this valuable information:

- The dearth of information about DR practices in this birthweight range of infants
- The known high potential for selection bias following the use of antenatal consent procedures.^{17, 18}

Data Collection for these infants will not include any HIPPA protected privileged information. We will be collecting the following information from parents who refused consent:

Data Collection Topic	Specific Data Elements
Delivery Room Data	Month/Year of birth; time of cord clamping (recorded as mm:ss after birth); birth weight; Apgar score at 1 and 5 min; gender; NRP guidelines used in the resuscitation of the infant such as respiratory status; procedures if any (intubation, chest compression, administration of epinephrine; surfactant delivery; UAC/UVC placement; chest tube placement; final respiratory status before leaving DR; and outcome of resuscitation.
Maternal Data Form	gravid para status, exposure to antenatal steroids and type; maternal ethnicity/race; antenatal corticosteroids (if yes, number of courses); any medications given to prolong pregnancy including tocolytics; diagnosis of diabetes during pregnancy (insulin dependent); placental abruption; chorioamnionitis; membranes rupture \geq 24 hours before delivery; mode of delivery

4.5.4. Training and Standardization of Research Intervention

A training video has been produced for use in training the staff at all participating clinical sites. (It will also be translated into Italian; neither the Dutch nor German sites will need translation). The video will be used to train the research team about the protocol but also can be viewed when the team has been alerted that a potentially eligible SAIL baby may be born shortly. This video can be accessed from the SAIL Trial Website which will be created and maintained by the DCC. Should any university site deem this an unsafe site, the video will be sent as a file to the respective hospital site coordinator to load on appropriate computers. Should any university site deem this an unsafe site, the video will be sent as a file to the respective hospital site coordinator to load on appropriate computers

To assess fidelity of the research intervention across sites, a variety of methods will be used.

- A main feature of our methods here hinge on the use of video recordings. Video capability during resuscitation for quality control purposes is available at UCSD, Calgary, Ulm, and Milan. A random sample of infants at each of these sites will be evaluated by the quality team (led by the Philadelphia team of Drs. [name], [name], [name], and [name]).
- A training checklist will be generated for those who perform SI and will include simulation. The PI at each site will be responsible to ensure that each person performing SI has been properly trained.

4.6. Random Allocation in the Delivery Room

Following informed consent, the mechanics of the randomization maneuver in the DR addresses the following aspects:

- Twins and multiples will be randomized as a unit, using a single envelope.
- Envelopes will be kept immediately outside the DR, at a safe designated site suitable for each site.

There will be between 3-5 envelopes for each of the gestational age strata in each location. This will ensure that in the hurry around a pending delivery there is no excess fumbling. Selection will be sequential and the lowest number marked on the envelope will be taken.

The next numbered envelope will be taken into the DR by the NICU-DR team. Opening of the envelope, and thus randomization, will only be performed when the infant has been delivered and deemed to require respiratory assistance. Within 15-30 seconds the assessment of whether or not the baby is eligible to be randomized is possible to make in a safe manner.

We have undertaken extensive simulation of this procedure and it does not introduce time-delays. We provide here a video clip showing this procedure in action at one of these simulations on the SAIL Trial website. Our procedure is modeled on those undertaken during the pivotal COIN trial where a member of our Steering Committee ([name] Melbourne) was a co-investigator. In addition [name] was one of the site investigators for the COIN trial at McMaster University, Canada, where the process of randomization also did not impede safe practices in the DR.

Thus opening of the envelope will not impede appropriate delivery of care. All opened envelopes and assignments will be kept in the logs of the site. The research study coordinator will be available as a back-up for the clinical Neonatal DR delivery team.

5. Study Data

The following is a table of details that will be collected, and it is itemized by day of collection. It should be noted that only the details of the sustained inflation maneuver itself, and the screening log for eligible patients, is unique to this study. All other data points are routinely measured. There are no blood tests or data being collected that are not already routine clinical data.

Data Collection Topic	Specific Data Elements	Specific time interval
Eligibility and Randomization Data Form	Clinical data: meets inclusion criteria and none of exclusion criteria; eligibility confirmed Research: date and time of randomization, and allocation of treatment arm (control vs intervention)	First 30 seconds of birth
Delivery Room (DR) Data Form	RESEARCH DATA collected: time infant is placed on resuscitation trolley; time of specific maneuver; 1 st sustained inflation and exact pressure measurement x 15 seconds; time of 2 nd sustained inflation and exact pressure measurement x 15 seconds; and use of ventilator vs T-piece	Research intervention takes place within the first 30 seconds up to 1 - 2 minutes of life
	Clinical data: time of birth, time of cord clamping, NRP guidelines used in the resuscitation of the infant such as respiratory status; blood gas values including glucose and hemoglobin/hematocrit values; procedures if any (intubation, chest compression, administration of epinephrine; surfactant delivery; UAC/UVC placement; chest tube placement and additional medications; final respiratory status before leaving DR; and outcome of resuscitation. Additional clinical information: date and time of birth, birth weight, Apgar score at 1 and 5 min, and gender	Certain clinical time points as dictated by the resuscitation process in the DR; data should be completed within first 48 hours

Data Collection Topic	Specific Data Elements	Specific time interval
Respiratory function measurements of inflations and physiologic monitoring (Obtained only at a subset of sites)	Inflation characteristics: pressure, flow, tidal volume, exhaled CO ₂ Physiologic monitoring: heart rate, oxygen saturation, delivered oxygen concentration	First 10 minutes of life
Delivery Room Video recording (obtained only at a subset of sites; transferred and destroyed after analysis)	Video recordings of the infant during the initial resuscitation and stabilization	Up to the first 30 minutes of life
Adverse Events	See Section 9.2 for detailed information.	Specific events during the first 10 days of life; thereafter continuing AE reporting structures are in place until the infant reaches 36 weeks GA
SNAPPE Score	Clinical data: severity score that is compiled by using clinical parameters within the first 12 hours of life, such as lowest pH, PaO ₂ and corresponding FiO ₂ and MAP, urine output and presence of seizures	Completed by first week of life
Daily Respiratory Status for First Week of Life	Clinical: current respiratory status at noon each day to include if applicable, respiratory support (CPAP, noninvasive PPV, invasive PPV); specific ventilatory settings; surfactant administration Infant's respiratory rate, highest FiO ₂ from previous time point and corresponding SpO ₂	Completed for every day for the first week of life

Data Collection Topic	Specific Data Elements	Specific time interval
Daily Assessment for First Week of Life	
Clinical: birth weight and head circumference; antibiotics, antifungals, indomethacin or ibuprofen, caffeine or other methylxanthines; furosemide or other loop diuretic; thiazide diuretic; corticosteroids, inhaled corticosteroids, inhaled nitric oxide, inhaled bronchodilator; vitamin A IM, erythropoietin; red blood cell transfusion, any paralytic agent; any anticonvulsants, any milk feed or formula, any breast feeding and any parental nutrition
 
Clinical radiographic data, if available: head ultrasound or MRI, number of CXR, abdominal films
	Completed for every day for the first week of life
Maternal Data Form	Clinical: mother's age, gravid para status, exposure to antenatal steroids and type; maternal ethnicity; maternal education, any medications given to prolong pregnancy including tocolytics; placental abruption; chorioamnionitis; membranes rupture ≥ 24 hours before delivery; mode of delivery	Completed within one week of enrollment
Weekly Respiratory Status until 36 wks PMA	
Clinical: current respiratory status at noon once/week to include if applicable, respiratory support (CPAP, noninvasive PPV, invasive PPV); specific ventilatory settings
 
Infant's respiratory rate, highest FiO₂ from previous time point and corresponding SpO₂
	Collected weekly from 2 nd week of life until 36 weeks PMA
Weekly Assessment until 36 wks PMA	Same as above with the exception of weekly head circumference instead of at birth and date of successful extubation defined as extubation for greater than 48 hours	Can be completed once a week (does not need to be a specific day of the week)
Respiratory Status at 36 wks PMA	
Clinical data: exact 36 wks PMA date; respiratory status (RA, NC, CPAP, invasive/non-invasive PPV),
 
If applicable pass/fail Oxygen Reduction Test (ORT)
	Can be completed within one week of reaching 36 wks PMA

Data Collection Topic	Specific Data Elements	Specific time interval
Discharge Status	Clinical data: date of discharge or death, co-enrolled in other clinical trials, and respiratory status	Once a baby has been discharged, reached 44 weeks PMA or died, whichever occurs first
Record of Death	Clinical: date of death, primary cause of death; autopsy performed, if yes, provide narrative	If applicable
Neonatal Outcome Data	Clinical data: PDA (treated Y/N), IVH (grade), ROP stage > 1, BPD, and positive blood culture sepsis, and other complications	Once a baby has been discharged, reached 44 weeks PMA or died, whichever occurs first
Late Outcome Data	Clinical data: final date of discharge, transfer or death if after 44 weeks PMA; reason for continued hospitalization beyond 44 weeks PMA	If applicable, for infants who remain in hospital past 44 weeks PMA
Transfer Form	Clinical data: date of transfer, transfer to medical facility, foster care, etc.	If applicable, for infants who are transferred to an outside facility prior to reaching 36 weeks PMA
Follow-up Assessment at 22-26 months cGA	Clinical data: the incidence of ambulatory and non-ambulatory CP defined by Gross Motor Function Score (GMFCS); hydrocephalus shunt, microcephaly, or seizure disorder; presence of respiratory disease necessitating readmission before 22-26 months follow-up; all individual components of the composite outcome of Neurodevelopment Impairment NDI or death, including cognitive outcomes at follow-up at 1 SD cut-off on the Bayley Scale of Infant Development BSID III standardized scales, BSID III cognitive, language and motor scores at 2 SD cut-offs (<70) at follow-up.	Once a baby has had a 22-26 month cGA follow-up visit in clinic

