6.1. Statistical Plan

6.1.1. Sample Size Determination

Sample size is based on a possible reduction in risk of neonatal mortality/BDP in infants at 36 weeks PMA receiving the SI intervention compared to those who receive the standard PEEP/CPAP. The significance level was set at $\alpha=0.038$ (due to the interim analyses), and power at 80%. Based on information from the recent multi-center NICHD SUPPORT trial² and the COIN trial,²⁰ we estimate that the baseline rate of neonatal mortality/BDP in the standard or care (control) arm by 36 weeks is 65%.

In order to detect an absolute risk reduction of 12.5%, 263 subjects per treatment arm are required. We anticipate virtually no loss to follow-up for the primary endpoint as infants will likely still be hospitalized because of their condition, will be under constant and continuing medical care. We have inflated the estimate by 1.12 to allow for twins and multiples to be randomized together. With this inflation in mind, the target sample size for this study is 300 subjects per arm.

For the secondary outcomes available in all subjects, with 263 subjects per arm (ignoring the twin correction factor), there will be 80% power to detect a difference of 0.24 standard deviation units in continuous outcomes, and a hazard ratio of 0.77 in survival outcomes under a proportional hazards assumption. Some secondary outcomes will not be available due to death of the infant, or loss to follow-up after discharge from the NICU. Overestimating these rates at 50%, we assume 130 subjects per arm will be available for the longer term secondary outcomes. With this sample size we will still have sufficient power to detect a clinically meaningful difference of at least 17% in event rates (or odds ratio of at least 2.0).

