- 25. Duration of respiratory support (ventilation, CPAP, supplemental oxygen) in days (SA9)

22-26 Months corrected gestational age:

- 26. Neurodevelopmental outcomes (SA14)
- 27. Respiratory outcomes (SA14)

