5. FINAL DATA ANALYSIS UPON COMPLETION OF TRIAL

Upon completion of the primary outcome at 36 weeks PMA, after all data has been entered in the database and query resolution is complete, the primary statistical analysis and description of the data will be performed. The final analysis for the 22-26 month cGA secondary outcomes will be completed separately, after that data has been entered in the database and cleaned. The staff biostatistician under the direction of the faculty biostatisticians will produce a final report outlining all analyses and interpretation of the results. This report will be used as the basis of the primary manuscript to be prepared for publication. Details of the analyses and statistical methods to be included in the final report are outlined below. All statistical tests described below will be conducted using a two-sided level of significance.

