5.4.3 Group Sequential Boundary for Primary Endpoint

To avoid inflating the overall Type I error rate for the primary analysis of efficacy, an O'Brien-Fleming boundary will be used to calculate the nominal significance level to which the interim p-value for the primary endpoint is compared. The efficacy boundary is 0.038 at the final analysis.

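### The 22-26 month Bayley-III outcomes are given a form only as cut-offs, and no mean-score comparison is assigned to them; cut-offs alone give up power that the SAP's existing linear GEE method would recover.

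*Protocol*

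**What the plan says.** - **Form of the outcome.** In protocol section 5 (Study Data), the row for the follow-up assessment at 22-26 months lists a 1 SD cut-off for cognition and "BSID III cognitive, language and motor scores at 2 SD cut-offs (<70) at follow-up". It places them among the components of the composite of neurodevelopmental impairment or death. SAP 2.1 likewise speaks of rates of impairment.
- **Power.** Protocol 6.1.1 introduces the later outcomes with "Overestimating these rates at 50" per cent, meaning death and loss to follow-up. It continues: "we assume 130 subjects per arm will be available for the longer term secondary outcomes". It then claims "sufficient power to detect a clinically meaningful difference of at least 17% in event rates (or odds ratio of at least 2.0". That statement serves all longer-term outcomes, respiratory ones included. The section's continuous-outcome figure (0.24 SD with 263 per arm) covers only outcomes available in every infant.
- **Analysis.** SAP 2.3.2 lists endpoint 26 as "Neurodevelopmental outcomes (SA14") and adds no scale, cut-off or model. Protocol 6.1.3 and SAP 5.4.2 send continuous secondary outcomes to linear regression, in the SAP with GEE where multiples require it. Neither names a Bayley score as one of those outcomes.

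**The concern.** Bayley-III composites are standardised scores. Reducing each one to above or below a threshold discards the information on how far an infant lies from it. Neither document gives a reason for relying on the cut-offs. The method for using the scores is already in the SAP, but nothing connects it to this endpoint.

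This visit supplies the trial's long-term neurodevelopmental evidence, and SAP 6.4 already says it will be an analysis of completers. If only proportions are compared, a moderate shift in scores in either direction could well go undetected. Because endpoint 26 is undefined, the choice between cut-offs and means could also be made after the data have been seen.

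**Working it through.** **Inputs from the documents.** n = 130 per arm (protocol 6.1.1), 1:1 allocation, and two-sided testing (SAP section 5: "All statistical tests described below will be conducted using a two-sided level of significance"). The alpha for secondary outcomes is not stated. The primary outcome uses 0.038 at the final look (SAP 5.4.3). I use 0.05 because it reproduces the plan's secondary figures.

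**Assumptions, not in the documents.** Normal scores with equal SD, a common shift d (in SD units) between arms, control rates below the cut of 10-65%, and multiples ignored unless stated.

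**Formulas.**
- Cut-off: power = Φ[(|p1−p2| − 1.96·√(2p̄(1−p̄)/n)) / √((p1(1−p1)+p2(1−p2))/n)], where p̄ is the mean of p1 and p2.
- Score: power = Φ[d·√(n/2) − 1.96].
- Link between them: d = |Φ⁻¹(p1) − Φ⁻¹(p2)|.

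**Step 1: reproduce the plan's figure.** For 50% against 33%, p̄ = 0.415 and the two standard errors are 0.0611 and 0.0602. Power = Φ[(0.17 − 1.96×0.0611)/0.0602] = Φ(0.834) = 0.798. The odds ratio is (0.50/0.50)/(0.33/0.67) = 2.03. So 17 points and an odds ratio of 2.0 agree with each other at mid-range rates. At alpha 0.038 the power is 0.763, so the figure fits 0.05. The 0.24 SD figure also fits 0.05: 2.80×√(2/263) = 0.244.

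**Step 2: the same 17-point difference on the scores.** From 50% to 33%, d = 0.440. Power = Φ(0.440×√65 − 1.96) = Φ(1.587) = 0.944, a gap of 14.6 points. Other control rates:

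| Control rate and change | d | Cut-off | Score | Gap (points) |
|---|---|---|---|---|
| 10% up to 27% | 0.67 | 0.946 | 1.000 | 5.4 |
| 15% up to 32% | 0.57 | 0.903 | 0.996 | 9.3 |
| 20% up to 37% | 0.51 | 0.863 | 0.984 | 12.1 |
| 30% up to 47% | 0.45 | 0.808 | 0.952 | 14.4 |
| 40% up to 57% | 0.43 | 0.786 | 0.934 | 14.7 |
| 50% up to 67% | 0.44 | 0.798 | 0.944 | 14.6 |
| 65% down to 48% | 0.43 | 0.793 | 0.940 | 14.7 |
| 40% down to 23% | 0.48 | 0.843 | 0.975 | 13.1 |
| 30% down to 13% | 0.60 | 0.920 | 0.998 | 7.8 |
| 20% down to 3% | 1.04 | 0.992 | 1.000 | 0.8 |

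**Step 3: a moderate shift, d = 0.35.** This is close to what 130 per arm can detect on the scores: (1.96 + 0.8416)×√(2/130) = 0.347 SD at 80% power. Score power = Φ(0.35×√65 − 1.96) = Φ(0.862) = 0.806. Cut-off power:

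| Control rate | Improvement | Harm |
|---|---|---|
| 10% | 0.316 | 0.425 |
| 15% | 0.393 | 0.495 |
| 20% | 0.452 | 0.540 |
| 30% | 0.533 | 0.592 |
| 40% | 0.582 | 0.610 |
| 50% | 0.606 | 0.606 |

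With the plan's 1.12 factor for multiples (130/1.12 = 116), score power is 0.760, against 0.49-0.56 for control rates of 30-50%.

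**Step 4: smaller differences, from a 50% control rate.** The gap is 14.6 points at a 17-point difference, 18.6 at 15, 20.0 at 12.5, 16.6 at 10, 11.8 at 8 and 4.8 at 5. It rises and then falls, because neither analysis has power against a very small shift.

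**Step 5: more infants followed.** At an illustrative 190 per arm, the gap at the 17-point difference is about 2-7 points for control rates of 30-50%. At d = 0.35 the same formulas give 0.927 on the scores, Φ(0.35×√95 − 1.96), against 0.70-0.77 on a cut at those rates.

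**The case against.** **The documents do not plan cut-offs only.** The quoted row belongs to a data-collection table, where the cut-offs help define the composite. The analysis sections allow linear regression for continuous outcomes, and endpoint 26 does not exclude scores. This stands: a reader might infer that score analysis is ruled out, and it is not. What remains is that a form is given only for cut-offs and rates, and no score is assigned to the linear method.

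**The plan does not expect to lose half its infants.** Protocol 6.1.1 calls its 50% an overestimate, and SAP 6.4 expects loss to follow-up to be minimal. This stands too: 130 per arm is a conservative floor, and Step 5 shows that the loss at the 17-point difference shrinks with better retention.

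**The 17-point target is not a Bayley target.** It is generic, and many of the other long-term outcomes (cerebral palsy, shunt, seizures, readmission) are naturally event rates. Powering those on rates is reasonable. The point is only that no figure is given for a score.

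**A mean-score comparison covers survivors only.** SAP 6.4 warns that the benefit of randomisation may not hold in completers, whereas the composite counts deaths. Assigned values for infants who cannot be tested would also depart from the normal model used here. Both limits are real. They are reasons to report the scores beside the composite and the cut-offs, not in place of them.

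**Conclusion.** The concern holds as a gap in endpoint definition with a real cost in power. At 130 per arm and a 0.35 SD shift, the scores have about 81% power. A cut has 53-61% with a 30-50% control rate and 32-54% with a 10-20% control rate.

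At a 17-point difference the loss is about 13-15 points for control rates of roughly 30-50% (an increase) or 40-65% (a fall). It is 5-12 points for an increase from 10-20%, and about 8 for a fall from 30%. A reader might infer that 13-15 points applies to the <70 cut-off in general, or that the loss keeps growing as the shift gets smaller. The documents support neither: they give no rate below 70, and the gap narrows for very small shifts.

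All these figures rest on normal scores, a common shift, two-sided alpha 0.05 and assumed control rates. At alpha 0.038 the loss for a 17-point fall from 40-65% would be 15.4-16.7 points. The change is worth making, but the gap does not touch the primary analysis.

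**What to change.** - In SAP 2.3.2 endpoint 26 and the protocol follow-up row, record the Bayley-III cognitive, language and motor composite scores as numbers.
- Compare mean scores between arms by linear regression with GEE for multiples (the SAP 5.4.2 method), and report each mean difference with its 95% CI.
- Keep the proportions below 1 SD and below 70, and the composite of impairment or death.
- Add to protocol 6.1.1 the detectable mean difference at 130 per arm: about 0.35 SD at 80% power, ignoring multiples.
- State how infants who cannot be tested are scored, and that the score analysis covers survivors and is read beside the composite, with the SAP 6.4 caveat.

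The cost is small: some wording and one model per composite, with no new assessment. It adds three secondary estimates. SAP section 5 analyses the 22-26 month outcomes separately from the primary outcome, and SAP section 8 allows amendments, so the change fits the plan's own process. It should be made before those data are examined.

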5.1. Maintaining Adherence to Algorithms and Minimizing Protocol Deviations

Extensive education and training will be undertaken to ensure technical proficiency and compliance with the protocol. A 'boot-camp' will be run at the start of the study by experienced study members ([name], [name], [name], [name], [name], [name], [name]). This will 'certify' the site PIs, who will then be in a position to train their own site-members. This training will be developed by the CCC Co-PIs and carried out locally by each site PI. A limited run-in period during

which SIs will be implemented in delivery room care will precede study initiation at each center in order to establish a level of comfort and overcome the learning curve effect. To further ensure adherence, we will complete a training video to be used as a refresher and training material for delivery room staff, fellows, and attendings. This will certify a site PI, who will be the gold standard trainer at her/his site. Site visits will be performed after 10 infants have been enrolled at each site, to examine site comfort and performance of the SI, as well as records kept, and trial functioning. At each site, a single SI per 2 months will be videotaped and reviewed at HUP for reproducibility and consistency. In addition, experts in simulation – [name], [name] and [name] will develop SI education.

